DNA	Deoxyribonucleic acid
DMID	Division of Microbiology and Infectious Diseases, NIAID, NIH, DHHS
DMP	Data Management Plan
DPO	Days post-illness onset
ELISA	enzyme-linked immunosorbent assay
ELISpot	Enzyme-linked immune absorbent spot
FDA	Food and Drug Administration
FDR	False discovery rate
FRNT	Focus Reduction Neutralization Test
FWA	Federalwide Assurance
FWER	Family-wise error rate
GCP	Good Clinical Practice
GEE	Generalized estimating equations
Hgb	Hemoglobin (blood test)
HIPAA	Health Insurance Portability and Accountability Act
HIPC	Human Immunology Project Consortium
HIV	Human Immunodeficiency Virus
ICF	Informed Consent Form
ICH	International Conference on Harmonisation
ICS	Intracellular Cytokine Staining
ICU	Intensive Care Unit
IDCRC	Infectious Diseases Clinical Research Consortium
IEC	Independent Ethics Committee
IFN	Interferon
IRB	Institutional Review Board
IVIG	Intravenous immunoglobulin

kg	kilogram
LAR	Legally authorized representative
MAR	Missing at random
MCAR	Missing completely at random
MERS-CoV	Middle Eastern Respiratory Syndrome virus
mg	milligram
mL	Milliliter
mmHg	Millimeter of Mercury
MOP	Manual of Procedures
N	Number (typically refers to subjects)
nAbs	Neutralizing antibodies
NETEC	National Emerging Special Pathogen Training and Education Center
NIAID	National Institute of Allergy and Infectious Diseases, NIH, DHHS
NIH	National Institutes of Health
NK cells	Natural killer cells
NSAID	Nonsteroidal Anti-Inflammatory Drug
OHRP	Office for Human Research Protections
PBMC	Peripheral Blood Mononuclear Cell
PaO ₂ /FiO ₂	Partial pressure oxygen/fractional inspired oxygen
PCR	Polymerase chain reaction
PD	Protocol Deviation
PI	Principal investigator
PRNT	Plaque reduction neutralization test
QA	Quality Assurance
QC	Quality Control
R	Correlation coefficient
RNA	Ribonucleic acid
ROC	Receiver operating characteristics
SARS-CoV-1	Severe Acute Respiratory Syndrome coronavirus 1
SARS-CoV-2	Severe Acute Respiratory Syndrome coronavirus 2
SBP	Systolic Blood Pressure
SCHARP	Statistical Center for HIV/AIDS Research and Prevention
SCID	Severe combined immunodeficiency
SDSU	Statistical and Data Science Unit
SOE	Schedule of Events
SOP	Standard Operating Procedure
TCR	T-cell receptor
US	United States
VTEU	Vaccine Treatment and Evaluation Unit
WGS	Whole genome sequencing

PROTOCOL SUMMARY

- Title:** Natural History and Immunological Response to Emerging Infectious Disease "X"
- Population:** Up to 1,000 participants¹ (male and female adults ≥ 18 years of age and male and female children < 18 years of age) with possible or definitive infection and/or close contacts to patients with possible or definitive infection with Pathogen "X" will be enrolled into one of two patient groups. Suspected cases may be based on appropriate exposure history and/or clinical presentation. Enrollment will be stratified by disease severity or other major categories of disease presentation as applicable.
- Group 1: Adults or children with confirmed or suspected Pathogen "X" infection representative of the disease spectrum
- Group 2: Adult or child close contacts of Pathogen "X" confirmed and/or suspected cases enrolled in Group 1
- Number of Sites:** Up to ten VTEU sites
- Study Duration:** Approximately 2 years from implementation of field activity through closure and analysis
- Participant Duration:** 12 months
- Objectives:** Primary:
- To characterize Pathogen "X" binding and neutralizing antibody responses by age and disease severity in study subjects.
 - To characterize T cell responses by age and disease severity.
 - To characterize B cell responses by age and disease severity.
 - To describe the clinical presentation and outcomes of Pathogen "X" infection in study subjects.

¹ Number of participants may be adjusted based on statistical considerations of Pathogen "X" and clinical manifestation.

Secondary:

- To describe innate immune responses to Pathogen “X”.
- To collect specimens for isolation of Pathogen “X” from body compartments pertinent to the pathogen.
- To determine rates of Pathogen “X” infection among close contacts of infected patients enrolled in Group 1.
- To determine the persistence of Pathogen “X” in whole blood, serum, urine, saliva, stool, or other body fluids as available (e.g., semen, vaginal secretions, breast milk) and characterize modes of pathogen shedding to support the development of diagnostic assays and public health prevention policy around transmission risk.

Exploratory:

- To characterize Pathogen “X”-specific immune responses other than classical antibody and T cell responses following Pathogen “X” infection to support vaccine development.
- To make available to the scientific community well-characterized specimens from Pathogen “X”-infected study subjects to facilitate development of diagnostic tests, vaccines, and therapeutics for use in other Pathogen “X” research.
- To collect large numbers of blood immune cells by leukapheresis from selected participants to establish a specimen bank for future detailed Pathogen “X” immunological studies.
- To evaluate the associations of Pathogen “X”-specific humoral and cellular immune responses with Pathogen “X” in whole blood, serum, exosomes, urine, saliva, stool and/or other body fluids as available (e.g., semen, vaginal secretions, breast milk).
- To sequence Pathogen “X” from collected specimens (blood, body compartments specific to Pathogen “X”, etc.) in a subset of participants for the study of within-host pathogen evolution.

Description of Study Design:

[figure not shown]
This is a prospective, observational, noninterventional cohort study designed to collect clinical information and specimens to evaluate innate and adaptive immune responses of patients with confirmed Pathogen “X” and their close contacts.

Estimated Time to Complete Enrollment:

2 years. This protocol will be shelf ready for specimen collection from potentially emerging pathogens over the life cycle of the current IDCRC.

SCHMATIC OF STUDY DESIGN

Total N: Up to 1,000 participants enrolled into one of two patient groups

2. BACKGROUND INFORMATION AND SCIENTIFIC RATIONALE

2.1 Background Information

The world has observed the emergence of a number of novel pathogens with geographic spread beyond original restrictions, and pandemics over the past 100+ years. Emergence of these novel pathogens has often occurred across the animal-human interface. Influenza has had a number of antigenic shifts occur including the 1918 influenza pandemic, H2N2, H3N2, H1N1, and p2009H1N1. Other influenza strains have also leapt into humans from animal populations including H5N1, H5N8, H7N9, and H3N2v. Human immunodeficiency virus (HIV) spread into the human population with initial descriptions of AIDS occurring in 1981. Outbreaks of Ebola continue to threaten various communities in Africa. Coronaviruses have spread into the human population with person-to-person transmission, including severe acute respiratory syndrome (SARS), Middle Eastern respiratory syndrome (MERS), and severe acute respiratory syndrome 2 (SARS-CoV-2) which causes coronavirus disease-19 (COVID-19). Geographic spread of viral pathogens has occurred well beyond their original borders including West Nile Virus, Zika, Chikungunya, dengue, and others. Both the 1918 influenza and the COVID-19 pandemics resulted in hundreds of thousands of deaths in the US and millions of deaths worldwide.

2.2 Scientific Rationale

With increasing world population, climate change, and globalization, it is likely that emergence and spread of new infectious threats will continue to occur and could result in potential pandemics. The National Institutes of Allergy and Infectious Diseases (NIAID) and the Vaccine Treatment and Evaluation Units (VTEUs) need to be ready to respond to such emerging threats through efforts to develop assays, understand the immunological response to infection, and develop new vaccines for these emerging pathogens. The proposed study aims to be ready to respond to the emergence or reemergence of a pathogen into the US (Pathogen “X”).

To determine the best approaches to advance vaccines and therapeutics, an understanding of the pathogenesis and immune responses to the infection in different populations is important. Collection of samples of the pathogen can be crucial to facilitating laboratory assay work, including development of pathogen diagnostics (e.g., PCR). Genome sequencing samples of the pathogen can also be used to study within-host pathogen evolution. Pathogen samples can also provide insight into persistence and transmissibility. Sampling close contacts (e.g., household) can provide additional insight into transmission patterns and provide adequate experimental controls. Detecting and describing the innate and adaptive (T and B-cell, antibodies, memory) responses to natural infection is needed to understand the kinetics and durability of such responses. In addition to the kinetics, the quality of the immune response may also be relevant, such as the neutralizing, non-neutralizing, and overall binding antibody

responses. Differences in the immunological response of various populations (e.g., age) and by disease severity could provide insights into markers of an effective immune response. This can ultimately help to identify potential correlates of protection against infection. For example, non-human primates infected with a live SARS-COV-2 or injected with either an RNA or DNA vaccine expressing the S protein developed neutralizing antibodies and were protected from subsequent live SARS-CoV-2 challenge.^{1,2} Description of these immunological responses from samples collected longitudinally from patients with specific disease severity and in different age groups is needed. It can also identify potential host differences due to genetic factors. Identifying these immunological responses can result in rapid advancement of new vaccines to address a new emerging pathogen.

For example, global mobilization occurred with the COVID-19 pandemic. The response to the challenge in the US was facilitated by rapid implementation of studies, communication of information, and combined efforts of the federal government, industry, academia, and many other institutions. This allowed the FDA to issue Emergency Use Approval for 2 vaccines about 11 months after the initial sequences from China were published, an unprecedented feat.^{3,4}

NIAID supports research critical to advancing human health and prevention of disease. VTEUs are a critical component of response (see Section 2.2.1). This protocol is written to stand 'at the ready' to be activated for the emergence of Pathogen “X” that could threaten national and/or global health.

2.2.1 VTEU Expertise

The VTEUs comprise 10 US sites with capacity to perform a wide variety of clinical studies and collect clinical information and specimens. A pilot study of Zika was conducted at Emory University, as well as a natural history study of Zika virus infection (DMID 16-0017 at Baylor, Emory and Saint Louis University VTEUs) for a rapid research response to Zika virus infections in US residents. Together these studies generated ground-breaking findings, resulting in publication of multiple manuscripts including case reports, viral shedding kinetics, innate and adaptive responses, and development of a Zika antibody dependent cellular cytotoxicity (ADCC) assay.⁵⁻¹¹ Although we are aware that other efforts are underway through other NIAID networks currently (e.g., NETEC, CEIRS, HIPC), we believe the VTEUs have a unique capacity to respond to the Pathogen “X” pandemic, given the VTEU’s demonstrated ability to enroll and follow patients both in and out of the hospital and given the prior experience of DMID 16-0017.

Development of this study by the Emory, Baylor, and Saint Louis University VTEUs (a joint effort combining efforts from several independently submitted concepts), based upon the framework of the prior DMID 16-0017, will provide the opportunity for standardized sample collection and testing and facilitate the development of vaccines and therapeutics. It could also provide important data about potential correlates of protection.

2.2.2 Importance and Impact

Unique aspects of this study include: 1) enrollment of patients representative of the disease spectrum with serial specimen sampling (including early time points) and long-term follow-up (e.g., memory immune response); 2) comparisons of different age cohorts spanning from childhood to the elderly; 3) investigations of close contacts ensuring earlier studies of innate and adaptive immunity; and 4) the collection of specimens for development of immunological assays and assessment of responses over time.

We believe that this study is critical for several reasons:

- It provides prospectively collected specimens from patients with well-defined time points that will enable the advancement of our understanding of the innate and adaptive responses to Pathogen “X”.
- The study includes both adults and children with Pathogen “X”. Data from children were by-in-large missing from the COVID-19 pandemic resulting in deprioritization of vaccine development in this population. Children have different immune responses to infection compared to adults and are critically important in the transmission of many different pathogens and could be relevant for Pathogen “X”.
- It has high value in collecting samples from close contacts, exposed subjects and/or suspected cases before Pathogen “X” infection occurs along with serial sampling to detect potential secondary transmission. Enrollment of close contacts is additionally valuable for identifying and studying cases of asymptomatic infection, which can be otherwise challenging. Samples from uninfected close contacts will also serve as controls.
- This study promises an opportunity to collect specimens that could be critical to future efforts to develop vaccines, assays and validation specimens.

2.3 Potential Risks and Benefits

2.3.1 Potential Risks

The potential risks of participating in this trial are those associated with having blood drawn, collection of other body fluid specimens, and leukapheresis (only for those adult volunteers consented for leukapheresis, see Sec 2.3.1.1).

Drawing blood may cause temporary discomfort and fainting. Fainting is usually transient and managed by having the subject lie down and elevate his/her legs. Bruising at the blood draw site may occur but can be prevented or lessened by applying pressure to the blood draw site for a few minutes after the blood is taken. Drawing blood may cause infection. The use of aseptic (sterile) technique will make infection at the site where blood will be drawn extremely unlikely.

A urinalysis is considered a safe and non-invasive form of testing. The only risk it may pose is for those who require catheterization to obtain a urine sample. The risks of urinary

catheterization include infection, bleeding, pain, and bladder damage. There are no known risks for collection of urine by routine clean catch methods.

Risks are minimal with a mouth swab. One may experience a dry area in the mouth at the site of swabbing for a short period of time (less than a few minutes). This dryness is transient and will resolve on its own.

The risks of collecting specimens from the upper respiratory tract using oropharyngeal and nasopharyngeal swabs include gagging, feeling uncomfortable and possible minor nosebleed afterwards. Complications of oropharyngeal and nasopharyngeal suction include hypoxia and bradycardia.

The risks of collecting specimens from the lower respiratory tract using bronchoalveolar lavage (BAL) (in which a bronchoscope is passed through the mouth or nose into an appropriate airway in the lungs, with a measured amount of fluid introduced and then collected for examination) include transient hypoxemia, post-BAL fever (seen in up to 30% of patients), bronchospasm, and very rarely pneumothorax.

Risks are minimal with a vaginal swab. There may be slight transient irritation or discomfort when the swab is placed in the vaginal vault at the time of sampling. This is an optional sample in the study. The sample will be collected by a vaginal swab and not by intracervical swabs. The sample will be collected either through self-swab (by the subject) or collected during a clinically indicated vaginal exam. For pregnant women, if there are concerns about rupture of membranes the vaginal swab will not be collected.

There are no known additional risks for a lactating woman who is already expressing breast milk to donate a small amount of breast milk.

Risks are minimal with self-semen collection. This is an optional sample in the study. One may feel embarrassment. To try to minimize this, subjects who agree to provide a semen sample will have access to a private room to obtain the sample or will be able to obtain the sample at home.

Participation in research may involve a loss of privacy. Subject records will be kept as confidential as possible under the law. Individual identity will not be used in any reports or publications resulting from this trial.

2.3.1.1 Risks of Leukapheresis (only for those adult volunteers consented for leukapheresis)

Leukapheresis may be associated with pain, bruising, and discomfort in the arms at the site of needle placement. Vasovagal episodes, characterized by transient hypotension, dizziness, nausea, and rarely syncope, are seen in less than 5% of procedures. Additional risks include increased pulse, seizures, and blood loss. Anticoagulants added to prevent the blood from clotting may lead to a sour taste in the mouth, mild muscle cramps and/or tingling sensation around the mouth, feet, or hands. Mild reactions may be seen in 30-50% of leukapheresis procedures and can usually be relieved by slowing or temporarily interrupting the procedure or administering calcium carbonate tablets.

A temporary decrease (1-2 days) in red blood cell count is common. Rarely, machine malfunction may result in the loss of a half pint to a pint of blood. Leukapheresis does not affect the blood's ability to form clots in the event of subsequent cuts or injuries.

2.3.2 Known Potential Benefits

There is no direct benefit to the subjects. There is potential benefit to society resulting from insights gained from participation in this study due to the emerging threat of the Pathogen "X" outbreak.

3. OBJECTIVES

3.1 Study Objectives Endpoints (Outcome Measures)

Table 1: Objectives and Endpoints (Outcome Measures)

Objectives	Endpoints
Primary	

 To characterize Pathogen “X” binding and neutralizing antibody responses by age and disease severity in study subjects 	
 Pathogen “X” neutralization assay (e.g., PRNT, FRNT) Pathogen “X” pseudoneutralization assay

 To characterize T cell responses by age and disease severity 	
 T cell ELISpot and/or ICS assays

 To characterize B cell responses by age and disease severity 	
 Memory B cell testing Plasmablast antibody secreting cells (ASCs) responses

 To describe the clinical presentation and outcomes of Pathogen “X” infection in study subjects 	
 Clinical symptoms, laboratory abnormalities, days of illness, residual clinical problems, survival/death
Secondary	

 To describe innate immune responses to Pathogen “X” 	
 Transcriptomics, flow cytometry, serum and/or culture supernatant cytokine ELISA

 To collect specimens for isolation of Pathogen “X” from body compartments pertinent to the pathogen 	
 PCR and/or cultures

 To determine rates of Pathogen “X” infection among close contacts of infected patients enrolled in Group 1 	
 Rates of Pathogen “X” detection among close contacts of infected enrolled subjects at enrollment and over follow-up

 To determine the persistence of Pathogen “X” in whole blood, serum, urine, saliva, stool, or other body fluids as available (e.g., semen, vaginal secretions, breast milk) and characterize modes of pathogen shedding to support the development of diagnostic assays and public health prevention policy around transmission risk 	
 Repeated PCR and/or cultures

Objectives	Endpoints
Exploratory	

 To characterize other Pathogen “X”-specific immune responses other than classical antibody and T cell responses following Pathogen “X” infection to support vaccine development 	
 Antibody Dependent Cellular Cytotoxicity, BCR repertoire, TCR repertoire, single cell phenotyping, targeted host genetic changes, immune response gene expression, and/or other endpoints relevant for Pathogen “X”

 To make available to the scientific community well-characterized specimens from Pathogen “X”-infected study subjects to facilitate development of diagnostic tests, vaccines, and therapeutics for use in other Pathogen “X” research 	
 Collection and storage of samples

 To collect large numbers of blood immune cells by leukapheresis from selected participants to establish a specimen bank for future detailed Pathogen “X” immunological studies 	
 Leukapheresis on selected subjects to obtain large numbers of blood immune cells for more detailed immunologic future studies

 To evaluate the associations of Pathogen “X”-specific humoral and cellular immune responses with Pathogen “X” in whole blood, serum, exosomes, urine, saliva, stool and/or other body fluids as available (e.g., semen, vaginal secretions, breast milk) 	
 PCR culture of specific samples or products derived from specific samples

 To sequence Pathogen “X” from collected specimens (blood, body compartments specific to Pathogen “X”, etc.) in a subset of participants for the study of within-host pathogen evolution. 	
 Whole genome sequencing (WGS) of Pathogen “X” from specimens collected in a subset of participants at enrollment and over time post-enrollment.

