6.2.2 Follow-up Visits and Final Visit

At intervals determined by the biologic characteristics after enrollment (up to 12 months)

Participants will undergo the following procedures as necessary:

- Collection of patient information including interval medical history, medications, and medical record review if available
- Collection of signs and symptoms of Pathogen “X” infection
- Review contact information
- Physical exam may be performed
- Vital signs may be collected as necessary
- Collection of specimens from body compartment specific to Pathogen “X”

Final Visit only

- Collection of biological specimens including, 10mL blood for serum from adults, 2.5 mL blood for serum from children.

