6.4 Laboratory Evaluations

6.4.1 Laboratory Evaluations/Assays

Laboratory testing will be conducted at potentially CLIA-certified laboratories and noncertified labs. Blood specimens and volumes will be obtained in accordance with the SOE (Appendix A). Blood specimens that will be collected as part of the standard specimen collection protocol will include serum and anticoagulated plasma both of which will be used for antibody testing and/or for measurement of circulating cytokines. Blood samples for isolation and cryopreservation of peripheral blood mononuclear cells (PBMCs) are collected for use in cellular and innate immune cell responses.

Specimens from body compartment specific to Pathogen “X” will be collected to test for Pathogen “X” detection.

Specimens will be collected for this study as indicated in the SOE and per detailed guidance provided in the MOP. Adult blood collection will not exceed 10.5 mL/kg or 550 mL, whichever is smaller, over any eight-week period. For participants with more severe Pathogen X disease, blood volumes drawn for PBMC harvests will be reduced from 60 mL to 24 mL for visits 1, 5 and 7 if the participant’s hemoglobin is ≤ 10 gm/dL, or if they have cardiogenic shock (defined as systolic blood pressure < 90 for > 30 minutes, requiring pharmacological vasopressor or mechanical support to maintain SBP > 90 , or Cardiac Index ≤ 2.2 L/min/m² and/or Pulmonary Capillary Wedge Pressure ≥ 15 mmHg), or severe hypoxemia (defined as PaO₂/FiO₂ < 100 or clinical evidence of end-organ ischemia). In addition, we will either reduce the blood volume taken to 24 mL or eliminate the PBMC blood draw on visits 1, 5 and 7, if in the opinion of the physician responsible for the participant’s care the planned blood draw would compromise the patient’s clinical status.

In accordance with US NIH recommendations, pediatric blood collection will not exceed 5 mL/kg in a single day or 9.5 mL/kg in any eight-week period.

Endpoint Assays

The specimens collected as part of this study will be available to the VTEU sites, DMID, and other interested parties as part of a specimen biobank. Certain assays may move forward as part of this study through the VTEU laboratories or IDCRC. Many of these assays may be under development across the VTEUs. With the emergence of new data, the protocol leadership and the IDCRC Leadership Group might decide to prioritize or de-prioritize some of these assays. These may include but are not limited to:

- Antibody assays:

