 - Pathogen “X” neutralization assay (e.g., PRNT, FRNT)
 - Pathogen “X” pseudoneutralization assay
 - Binding antibody assays
 - Serology for related pathogens

- Pathogen “X” detection assays:
 - Pathogen “X” detection assays (e.g., PCR, culture)
- T cell responses
 - T cell ELISpot and/or ICS assays
- B Cell responses
 - Memory B cell testing
 - Plasmablast antibody secreting cells (ASCs) responses
- Innate immune responses (e.g., transcriptomics)
- Pathogen “X” whole genome sequencing (WGS)

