7.2.2 Power Analysis for Response Rates

The immune responses will also be analyzed by estimating response rates in Group 1 overall and in subgroups of Group 1 participants defined by baseline subject characteristics such as age and disease severity. Examples of response rates include the proportion of XXX. The study may also estimate the rate of Pathogen “X” infection among Group 2 participants, i.e. close contacts of Pathogen “X”-positive enrolled subjects.

The precision with which the true response rate can be estimated from the observed data depends on the true underlying response rate and the sample size (n). Two-sided 95% confidence intervals for the response rate based on observing a particular rate of response are presented in Table X for a variety of scenarios.

Table X: Two-sided 95% confidence intervals for the true response rate based on observing a particular rate of responses

Sample size	Number of responses	Response rate	95% confidence interval (in %)

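### The contact endpoint in Table 1 counts pathogen detection while its objective is infection, so infections cleared before enrollment or detectable only between visits are missed and the rate is biased downward

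*Protocol*

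**What the plan says.** Table 1 (Protocol, Section 3.1) sets the secondary objective "To determine rates of Pathogen “X” infection among close contacts of infected patients enrolled in Group 1" and pairs it with the endpoint "Rates of Pathogen “X” detection among close contacts of infected enrolled subjects at enrollment and over follow-up". Section 7.2.2 again speaks of infection: "The study may also estimate the rate of Pathogen “X” infection among Group 2 participants".

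Section 6.4.1 explains what detection means. It states "Specimens from body compartment specific to Pathogen “X” will be collected to test for Pathogen “X” detection" and has a list entry reading "Pathogen “X” detection assays (e.g., PCR, culture"), set apart from the antibody assays, which include binding antibody.

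Section 2.2.2 gives two uses for contacts: "Enrollment of close contacts is additionally valuable for identifying and studying cases of asymptomatic infection", and "Samples from uninfected close contacts will also serve as controls". No section defines an infected or an uninfected contact.

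Section 6.2.2 places contact visits "At intervals determined by the biologic characteristics after enrollment (up to 12 months"), so the spacing is open. Contacts give serum and PBMCs on Day 1 (Section 6.2.1, Table 3) and one later serum. Table 3 limits that serum to Day 14; Section 6.2.2 lists it under the final visit alone. No later PBMC draw is scheduled for contacts.

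**The concern.** Infection and detection are different quantities when sampling is intermittent. A contact can be infected and never yield a positive specimen, either because the pathogen was cleared before Day 1 or because it was detectable only between two visits. Both routes are open here. Contacts are approached only after the index case is enrolled (Section 4), the eligibility criteria (Section 5.2) set no limit on time since exposure, and visit spacing is not fixed.

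Two things are at stake. The contact infection rate, a secondary objective, would be underestimated, and enrolling more contacts would not help, because a larger sample narrows the interval around the wrong value. Asymptomatic infection, a stated reason for enrolling contacts, is the case most exposed, since no symptoms prompt extra testing. Second, with no definition of an uninfected contact, someone already infected or recovered on Day 1 but detection-negative could be used as a control.

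**Working it through.** **No planned figure to reproduce.** The response-rate table in Section 7.2.2 is an unfilled template. The protocol gives no contact infection rate, detection sensitivity, shedding duration or visit interval.

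**Step 1: the texts side by side.**
- Objective (Table 1) and Section 7.2.2: infection.
- Endpoint (Table 1): detection.
- Section 6.2.1 says body-compartment specimens from contacts are taken to test for infection; Section 6.4.1 says such specimens are for detection. As written, infection status therefore rests on detection.
- Serology: two contact sera are scheduled and binding antibody assays are listed, but neither is tied to infection status.

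**Step 2: direction.** Let p be the true infection rate and s the share of infections ever detected. With no false positives, the expected reported rate is p × s and the error is −p(1 − s). It cannot be positive, and is zero only if s = 1.

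**Step 3: what s depends on.** For one detectable period of W days and visits D days apart, s = min(1, W/D). W and D are assumptions:

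| W (days) | D = 7 | D = 14 | D = 30 | D = 90 |
|---|---|---|---|---|
| 7 | 1.00 | 0.50 | 0.23 | 0.08 |
| 14 | 1.00 | 1.00 | 0.47 | 0.16 |
| 21 | 1.00 | 1.00 | 0.70 | 0.23 |

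Frequent visits or long shedding remove the between-visit loss. They do not recover infections cleared before Day 1.

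**Step 4: illustration of the rate.** Assume p = 20% and use the 95% score interval planned in Section 7.4.2 for crude rates. N = 1000 is the Group 2 figure in Section 7.3; N = 500 is added because up to 1,000 is elsewhere the total for both groups.

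| s | Reported rate | Interval, N = 1000 | Interval, N = 500 |
|---|---|---|---|
| 0.9 | 0.20 × 0.9 = 18.0% | 15.7–20.5% | 14.9–21.6% |
| 0.7 | 0.20 × 0.7 = 14.0% | 12.0–16.3% | 11.2–17.3% |
| 0.5 | 0.20 × 0.5 = 10.0% | 8.3–12.0% | 7.7–12.9% |

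For p of 10%, 20% and 40%, the interval excludes the true rate at s = 0.7 and s = 0.5 for both N. At s = 0.9 it contains the true rate in five of six cases; the exception is p = 40%, N = 1000. These intervals treat contacts as independent; correlation among contacts of one index case would widen them.

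**Step 5: controls.** Contact PBMCs are drawn on Day 1 only. A contact infected afterwards was still uninfected when those cells were taken. The exposed group is contacts already infected or cleared by Day 1 and detection-negative then. The share p(1 − s)/(1 − ps) counts every missed infection whenever acquired, so it does not estimate contamination of Day 1 cells and is not reported here.

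**Step 6: effect of adding serology.** Assume p = 20%, s = 0.7, and independent serology of sensitivity 80–95% with perfect specificity. The combined share found is 1 − 0.3 × 0.20 = 0.94 to 1 − 0.3 × 0.05 = 0.985, so the reported rate is 0.20 × 0.94 = 18.8% to 0.20 × 0.985 = 19.7%. Each percentage point of specificity lost adds up to 0.80 × 0.01 = 0.8 points of false positives.

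**The case against.** The strongest case is that an objective names a concept and an endpoint its measurement, so the pairing is not in itself a contradiction. This is a template held ready for an unnamed pathogen. Its assay list is open, contact visits are to be spaced to suit the pathogen, and the definition of a contact infection could come in a pathogen-specific version or an SAP. Section 7.2.2 says only that the contact rate may be estimated. Serology for a new pathogen may be unavailable or non-specific.

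Part of this stands. Spacing fitted to the pathogen could make the between-visit loss small, and no size can be asserted. It does not clear the endpoint: the objective says the rate is to be determined, Table 1 fixes detection as the measure, and an SAP that added serology would depart from that endpoint. Visit spacing also cannot recover infections that ended before Day 1.

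Two stronger readings are tempting and not supported. A reader might infer that every missed infection enters the control set. The protocol never says detection-negative contacts are the controls, and infections after Day 1 leave the Day 1 PBMC material unaffected; a later serum that is assayed for antibody could itself show infection. A reader might also infer that case-versus-control immune comparisons are diluted throughout. The primary immune objectives are by age and severity, the primary Group 1 analysis is by level of care (Section 7.1), and Section 7.4.2 allows group comparisons without specifying one of cases against uninfected contacts.

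**Conclusion.** The mismatch is on the page and worth correcting before activation. Table 1 measures detection for an objective about infection, and no text brings contact serology into infection status. The bias in the rate is downward, provided detection has no false positives. Its size is unknown: the illustrated reported rates of 10% to 18% against an assumed true 20% rest wholly on assumed p and s, and the loss could be near zero with frequent sampling or long shedding.

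The control problem is narrower. It is a possibility created by the missing definition of an uninfected contact, and for PBMCs it is confined to contacts already infected or cleared by Day 1. This concerns a secondary endpoint and does not touch the primary objectives by age and severity.

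**What to change.** **First**, reconcile the timing of the second contact serum between Table 3 and Section 6.2.2. It decides which infections seroconversion can show: a draw close to Day 1 misses infections acquired around or after it, and a late one leaves a long gap between paired samples.

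**Then**, in Table 1:
- Define an infected contact as detection in any study specimen, or seroconversion (or a prespecified titre rise) between the Day 1 serum and the scheduled follow-up serum.
- Report the detection-only rate as a supporting result.
- Report contacts who are seropositive but detection-negative on Day 1 separately.
- Define uninfected controls as negative on both measures when the control sample was drawn.

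**Cost.** Revised endpoint wording, one reconciled schedule entry, and a binding antibody assay of a kind already listed in Section 6.4.1, run on two sera already planned. No extra blood is needed. The downside is that the composite rate waits for a usable serology assay and depends on its specificity; the detection-only rate can be reported meanwhile.
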